the first	dose of each trial j	part, and	art, and viral and pregnancy tests can be performed within 7 days prior to are first days of each dual part, pregnancy tests need to be performed within 21 days prior to art, and viral and pregnancy tests can be performed outside hospital) can be used for screening assessments without the need for the same tests during the screening														
period. I	Patients who fail t	I the initial screening may not be rescreened (only once) until consultation with the Sponsor's designated medical representative and approval by the Sponsor.															
e. Height v	will be measured o	a only at Screening and weight will be measured pre-dose every cycle except Screening.															
f. Biochen	nistry tests include	ed aspart	ate amir	otransfe	rase (AS	T), alani	ne amino	otransfer	ase (AL'I	l'), γ-glut	tamyltran	sterase (γ-GT), I	actate de	hydrogen	nase (LDH), cholester	ol (TC), triglyceride
(1G), to	otal bilirubin (TBI	L), direc	t bilirut	$\frac{1}{1}$	L), total	protein ((TP), alb	umin (A	(LB), alk	aline ph	osphatas	e (ALP)	creating	e kinase	(CK), gl	ucose (GLU), uric ac	id (UA), blood urea
nitrogen	(BUN)/urea (Ure	ea), creat	inine (Ci	r), sodiur	n (Na), p	otassium	1 (K), cal	icium (C	a), phosp	onorus (P), magne	sium (M	g), and c		(CI). The	e first dose was admini	istered within / days
alter the	e examination dur	ing the s	creening	g period,	and 11 u	te dose v	was not a	ing on F	ered alle	r / days	of the e	xaminati	on and t	ne inves	ligator as	ssessed that re-judgm	ent was required, an
addition	lar examination co	ite blood		RC) red	blood of	$\frac{11}{PBC}$) here aos	lobin (H	b) plote	ach cycl	hemato	1 Day 10	T) neutr	onhil (N	EU) eos	inophil (EOS) becop	hil (BAS) monocrite
g. (MON)	lymphocyte (LV	M etc.	hemato	logy in (Vole 1	is schedu	iled on I) 1 (11 Day 1 (11	vithin 24	hours by	efore dos	sing) Da	v = 5 Day	v 10 Da	$v_{12} D_{2}$	w 15 and baseline be	ematology should be
perform	ed within 24 hour	s before	the first	study de	se hem	atology i	n other of	vcles is	nerforme	ed on Da	vs 1 and	10 of ea	ch cycle	and the	e examina	ation on Day 1 of eacl	h cycle is performed
before d	losing. Subjects w	ere eligi	ole for cl	hemother	apy adm	inistratic	on as det	ermined	by predo	se hemat	tology re	sults on	Day 1 of	each cv	ele.	ation on Day 1 of each	n eyele is periorinea
h. Urine ex	xamination include	es urine i	protein.	urine pH	urine ke	tone boc	ly, urine	glucose.	urine rec	d blood c	ells, urin	e white l	blood cel	ls, etc. T	he first d	lose is administered w	ithin 7 days after the
examina	ation during the sc	reening	period. I	f the dos	e is not a	dministe	red after	7 days o	of the exa	mination	n and the	investig	ator con	siders it	necessary	y to make a re-judgme	ent, an additional test
may be	performed from C	ycle 2, b	efore ad	ministrat	tion on E	ay 1 of e	each cycl	e, and or	n Day 10			0			5	, ,	
i. Women	of childbearing p	otential o	only.			-	-		-								
j. Baseline	e imaging was per	formed v	within 2	l days pr	ior to the	e first dos	se, every	$6 \pm 1 \text{ w}$	eek after	the first	dose, or	more fre	equently	if clinica	ally indic	ated. Imaging examin	ations should follow
calendar	r days and should	l not be	modified	l for trea	atment d	elays or	terminat	ions, and	d subject	ts who d	iscontinu	ie study	drug for	unaccep	ptable to:	xicity or other reason	s other than disease
progress	sion should contin	ue to be	followe	d for tun	nor asses	sments u	intil dise	ase prog	ression,	receipt o	f new an	tineoplas	stic thera	py, with	drawal fi	rom the study, or deat	th, whichever occurs
first.						C1	(D1										
k. For Cyc	te I only, blood sa	ampling	time poir	nts are do	etailed in	Chapter	6 Pharm	acokine	tics.	1 • • .		1.	20 .	т.,	11 / 1	1 111 1	1 (240 / 2
I. Chemot	herapy: Topotecar	1 WILL be	adminis	tered at 1	.25 mg/1	n∸ on Da	iys 1-5 of	t each 21	-day cyc	le via inf	travenous	s drip ov	r 30 mm	i; Irilaci	cilb/plac	ebo: will be administe	ered at 240 mg/m ² on 1×10^{-1}
Days I-	5 of each 21-day	cycle via	i intrave	nous drip	o over 30	min usi	ng 3% g	iucose ii	ijection (or norma	i saline a	as 250 m	L solutio	on before	e chemotl	nerapy due to PK stuc	iy. The first of these

Product: Trilaciclib Protocol Number: B02B00801-TRILA-301

Protocol Nu	mber: B02B00)801-TR	ILA-301				Jiangs	su Simce	re Pharm	naceutica	l Co., Lte	d					
	Screenin g Period			(2	21 days Cy	s per cy cle 1	Tr cle unt	eatmen il disea	it Perio ise prog	d ^a ;ression	ı or inte C	olerabl ycle 2 8	e) and abc)ve		Safety Visit ^b	Survival Follow-up ^c
	D-21 ~ - 1	D1	D2 D3 D4 D5 D10 D12 D15 D1 D2 D3 D4 D5 D10 + 30 days Every 60 days														
Window (Days)			$\begin{array}{ c c c c c c c c c c c c c c c c c c c$														
subjects wil drug (Trilad m. Hepatitis E (HBcAb), !	 subjects will receive Trilaciclib plus Topotecan and the second will likely receive Trilaciclib or placebo plus Topotecan. Date of medication visit is based on the first dose of investigational drug (Trilaciclib/Placebo) in each cycle (D1). m. Hepatitis B and C screening were performed during the screening period, five items of hepatitis B: if hepatitis B surface antigen was positive or hepatitis B core antibody was positive (HBcAb), HBV-DNA should be added; hepatitis C examination: if hepatitis C antibody was positive, HCV-RNA should be added. 																

Product: Trilaciclib Protocol Number: B02B00801-TRILA-301

5.3. Appendix 3 Criteria for CTCAE judgment of laboratory parameters

Laboratory parameters will be graded primarily using CTCAE version 5.0. CTCAE grading of some indicators cannot be based on CTCAE Version 5.0, requires clinical diagnosis or clinical diagnosis and value determination, and cannot be completely divided by programming, such as hyperglycemia, hypokalemia, hypophosphatemia, hyponatremia and hyperuricemia, which will be graded using CTCAE Version 4.03.

Parameter	Level				
	1	2	3	4	5
Albumin	< lower limit of normal – 3 g/dL; < lower limit of normal – 30 g/L	< 3 – 2 g/dL; < 30 – 20 g/L	< 2 g/dL; < 20 g/L	Life-threatening; urgent intervention indicated	Death
ALP Alkaline phosphatase	 > upper limit of normal - 2.5 times upper limit of normal (normal baseline); 2 to 2.5 times baseline (abnormal baseline) 	> 2.5 to 5.0 times the upper limit of normal (normal baseline); > 2.5 to 5.0 times the baseline (if abnormal baseline)	 > 5.0 to 20.0 times upper limit of normal (normal baseline); > 5.0 to 20.0 times baseline (if abnormal baseline) 	 > 20.0 times upper limit of normal (normal baseline); > 20.0 times baseline if baseline is abnormal 	-
ALT Alanine Aminotransferas e	 > upper limit of normal - 3 times upper limit of normal (normal baseline); 1.5 to 3.0 times baseline (if abnormal baseline) 	3 to 5 times the upper limit of normal (normal baseline), > 3.0 to 5.0 times baseline (if baseline is abnormal)	5 to 20-fold (if baseline is normal); > 5 to 20-fold (if baseline is abnormal)	 > 20 x upper limit of normal (if baseline is normal); > 20 x baseline (if baseline is abnormal) 	-
AST Aspartate Aminotransferase	 > upper limit of normal - 3 times normal Upper limit (normal baseline); baseline 	> 3-5 times upper limit of normal (normal baseline);	 > 5.0 - 20.0 of upper limit of normal Fold (normal baseline); > baseline 	> 20.0 times upper limit of normal (normal baseline);	-

Product: Trilaciclib Protocol Number: B02B00801-TRILA-301

Protocol Number:	B02B00801-TRILA-301	Jiangsu Simcere Pharm	aceutical Co., Ltd		
Transaminase	1.5 to 3.0 times (if baseline	> 3.0 - 5.0 of baseline Fol	5.0-20.0 fold (if baseline is	> 20.0 times baseline if	
	value is abnormal)	(Abnormal Baseline) d	abnormal)	baseline is abnormal	
	S	> 200 400 mg/41 7 75 On >	> 400 500 - / 11 10 24	> 500 m = / 11 = m > 12.02	
Hypercholesterole	$>$ upper limit of normal ~ 300	> 300 - 400 mg/dL / ./3 Or >	> 400 - 500 g/dL 10.34 - Or >	> 500 mg/dL or > 12.92	-
IIIIa	mg/dL or > upper limit of	- 10.34 mmol/L	12.92 mmol/L	mmol/L	
	normal ~ 7.75 mmol/L				
Hypertriglyceride	150 mg/dL to 300 mg/dL or	> 300 mg/dL to 500 mg/dL	> 500 mg/dL to 1000 mg/dL	Life Threatening	Death
mia	1.71	or $> 3.42 \text{ mmol/L to } 5.7$	or > 5.7 mmol/L to 11.4	C	
	mmol/L to 3.42 mmol/L	mmol/L	mmol/L		
Blood bilirubin	$>$ upper limit of normal ~ 1.5	Greater than 1.5 to 3.0 times	Greater than 3.0 to 10 times the	Greater than 10 times upper	-
increased	times upper limit of normal	the upper limit of normal	upper limit of normal (normal		
	(normal baseline); $> 1 \sim 1.5$	(normal baseline); greater than	baseline); greater than 3.0 to 10	(normal baseline); greater	
	times baseline (abnormal	1.5 to 3.0 times the baseline	times the baseline (abnormal	than 10 times baseline	
	baseline)	(abnormal baseline)	baseline)	(abnormal baseline)	
Creatinine	> upper limit of normal ~ 1.5	> 1.5 - 3.0 x baseline; > 1.5 -	> 3.0 times baseline value; >	> 6.0 x upper limit of normal	-
increased	times upper limit of normal	3.0 x normal	$3.0 \sim$		
	11	Limit	6.0 x upper limit of normal		
					D. d
Creatinine	Creatinine clearance (CrCl)	$\operatorname{CrCl} 59 \sim 30$	$\operatorname{CrCl} 29 \sim 15$	CrCl Small in 15	Death
clearance rate	less than 60 mL/min/1.73 m2	mL/min/1.73 m2	mL/min/1.73 m2	mL/min/1.73 m2; requiring	
(CrCl)				dialysis or renal transplant	

Product: Trilaciclib Protocol Number: B02B00801-TRIL A-301

Protocol Number:	B02B00801-TRILA-301	Jiangsu Simcere Pharm	aceutical Co., Ltd		
Hypercalcaemia	Corrected serum calcium >	Corrected serum calcium >	Corrected serum calcium > 12.5	Corrected serum calcium >	Death
(Corrected for	upper limit of normal ~ 11.5	11.5 - 12.5 mg/dL;	- 13.5 mg/dL; > 3.1 - 3.4	13.5 mg/dL; > 3.4 mmol/L;	
albumin)	mg/dL; > upper limit of	> 2.9 - 3.1 mmol/L; calcium	mmol/L; calcium	ionized calcium	
	normal	concentration $> 1.5 - 1.6$	concentration $> 1.6 - 1.8$	concentration > 1.8 mmol/L;	
	Limit: $\sim 2.9 \text{ mmol/L};$	mmol/L; symptomatic	mmol/L; hospitalization	life-threatening	
	Ionized calcium		required		
	concentration > upper limit of				
	normal $\sim 1.5 \text{ mmol/L}$				
Hypocalcemia	Corrected serum calcium <	Corrected serum calcium < 8.0	Corrected serum calcium < 7.0	Corrected serum calcium <	Death
(Corrected for	lower limit of normal ~ 8.0	- 7.0 mg/dL; < 2.0 - 1.75	- 6.0 mg/dL; < 1.75 - 1.5	6.0 mg/dL; < 1.5 mmol/L;	
albumin)	mg/dL; < lower limit of	mmol/L; calcium concentration	mmol/L; calcium concentration	ionized calcium	
	normal ~ 2.0 mmol/L; calcium	< 1.0	< 0.9	concentration < 0.8 mmol/L;	
	concentration	$\sim 0.9 \text{ mmol/L}; \text{ symptomatic}$	~ 0.8 mmol/L; hospitalization	life-threatening	
	< lower limit of normal ~ 1.0		required		
	mmol/L				
CK creatine	> upper limit of normal ~ 2.5	> 2.5 x upper limit of normal	> 5 x upper limit of normal to	> 10 x upper limit of normal	-
phosphokinase	times upper limit of normal	to 5 x upper limit of normal	10 x upper limit of normal		
Gamma glutamyl	> 1 to 2.5 times the upper limit	$>$ 2.5 \sim if baseline value is	$>$ 5.0 \sim if baseline value is	> 20.0 x upper limit of	-
transferase	of normal if baseline is normal	normal	normal	normal if baseline is normal	
(GGT)	or 2.0 to 2.5 times the baseline	5.0 x upper limit of normal; >	20. times the upper limit of	or > 20.0 x baseline if	
	level if baseline is abnormal	2.5 to 5.0 x baseline if baseline	normal; if the baseline value is	baseline is abnormal	
		is abnormal	abnormal, $> 5.0 \sim 20.0$ times		
			the baseline level		

Product: Trilacicl Protocol Number:	ib B02B00801-TRILA-301	Jiangsu Simcere Pharm	aceutical Co. Ltd		
Hyperglycemia (CTCAE 4.03)	Fasting blood glucose greater than upper limit of normal - 160 mg/dL or Fasting blood glucose greater than upper limit of normal - 8.9 mol/L	Empty abdominal blood glucose greater than 160-250 mg/dL or fasting plasma glucose greater than 8.9-13.9 mol/L	Empty abdominal blood sugar greater than 250-500 mg/dL or fasting plasma glucose greater than 13.9-27.8 mol/L	Fasting glucose greater than 500 mg/dL or 27.8 mol/L	-
Hypoglycemia	< lower limit of normal ~ 55 mg/dL; < lower limit of normal ~ 3.0 mmol/L	< 55 - 40 mg/dL; < 3.0 - 2.2 mmol/L	< 40-30 mg/dL; < 2.2-1.7 mmol/L	< 30 mg/dL; < 1.7 mmol/L; life- threatening; seizure	Death
Hemoglobin	Hemoglobin < lower limit of normal ~ 10.0 g/dL; < lower limit of normal ~ 6.2 mmol/L; < lower limit of normal ~ 100 g/L	Hemoglobin < 10.0 - 8.0 g/dL; < 6.2 - 4.9 mmol/L; < 100 - 80 g/L	Hemoglobin < 8.0 g/dL; < 4.9 mmol/L; < 80 g/L; transfusion indicated	Life-threatening; urgent treatment required	Death
Lipase increased	 > 1.5 x upper limit of normal (ULN) ULN 	> 1.5 - 2.0 x ULN; > 2.0 - 5.0 x ULN and asymptomatic	> 2.0 - 5.0 times ULN with signs or symptoms; > 5.0 times ULN but no symptoms	> 5.0 x ULN with signs or symptoms	-
Hyperkalemia	> upper limit of normal ~ 5.5 mmol/L	> 5.5 - 6.0 mmol/L; intervention	> 6.0 - 7.0 mmol/L; hospitalization required	> 7.0 mmol/L; life- threatening	Death
Hypokalemia (CTCAE 4.03)	< lower limit of normal (LLN) to 3.0 mmol/L	-	< 3.0 - 2.5 mmol/L	< 2.5 mmol/L	-

Protocol Number: B02B00801-TRILA-301 Jiangsu Simcere Pharmaceutical Co., Ltd $< 800 - 500/\text{mm}^3$; < 0.8 - 0.5 $< 500 - 200/\text{mm}^3$: $< 200/\text{mm}^{3}$: < lower limit of normal ~ Lymphocyte $800/\text{mm}^3$: count $x 10^{9}/L$ $< 0.2 \times 10^{9}/L$ $< 0.5 - 0.2 \times 10^{9}/L$ < lower limit of normal ~ 0.8 x $10^{9}/L$ < lower limit of normal ~ $< 1500 - 1000/\text{mm}^3$; < 1.5 - $< 1000 - 500/\text{mm}^3$; < 1.0 - 0.5Neutrophil count $< 500/\text{mm}^{3}$; _ $1500/\text{mm}^{3}$: $1.0 \times 10^{9}/L$ x 10⁹/L $< 0.5 \times 10^{9}/L$ < lower limit of normal ~ 1.5 x $10^{9}/L$ < lower limit of normal ~ 2.5 < 2.5 - 2.0 mg/dL or < 0.8 -< 2.0 - 1.0 mg/dL or < 0.6 - 1.0 mg/dL< 1.0 mg/dL or < 0.3 mmol/L -Hypophosphate mia (CTCAE mg/dL or < lower limit of 0.6 mmol/L0.3 mmol/L4.03) normal ~ 0.8 mmol/LHypomagnesemia | < lower limit of normal ~ 1.2 < 1.2 - 0.9 mg/dL; < 0.5 - 0.4 < 0.9 - 0.7 mg/dL; < 0.4 - 0.3< 0.9 - 0.7 mg/dL;Death mg/dL; < lower limit of normal mmol/L mmol/L < 0.4 - 0.3 mmol/L $\sim 0.5 \text{ mmol/L}$ Hypermagnesaem > upper limit of normal ~ 3.0 -> 3.0 - 8.0 mg/dL;> 8.0 mg/dL; > 3.30 mmol/L; Death ia mg/dL; > upper limit of normal > 1.23 to 3.30 Life Threatening ~ 1.23 mmol/L mmol/L < lower limit of normal < 75.000 to 50.000/mm³: < 50.000 to 25.000/mm³: $< 25.000 / \text{mm}^{3}$: Platelet count _ $75,000/\text{mm}^3$; < lower limit of < $75.0 - 50.0 \times 10^9/\text{L}$ $< 25.0 \text{ x } 10^{9}/\text{L}$ $< 50.0 - 25.0 \times 10^{9}/L$ normal ~ 75.0 x 10 $^{9}/L$

Product: Trilaciclib

Product: Trilaciclib Protocol Number: B02B00801-TRILA-301

Protocol Number:	B02B00801-TRILA-301	Jiangsu Simcere Pharmaceutical Co., Ltd					
Hypernatremia	> upper limit of normal ~ 150 mmol/L	> 150 - 155 mmol/L; intervention	> 155 - 160 mmol/L; hospitalization required	> 160 mmol/L; life- threatening	Death		
Hyponatremia (CTCAE 4.03)	< lower limit of normal ~ 130 mmol/L	-	130 to 120 mmol/L with or without symptoms	< 120 mmol/L	-		
Leucocyte	< lower limit of normal ~ 3000/mm ³ ; < lower limit of normal ~ 3.0 x 10 ⁹ /L	< 3000 - 2000/mm ³ ; < 3.0 - 2.0 x 10 ⁹ /L	< 2000 - 1000/mm ³ ; < 2.0 - 1.0 x 10 ⁹ /L	< 1000/mm ³ ; < 1.0 x 10 ⁹ /L	-		

Product: Trilaciclib Protocol Number: B02B00801-TRILA-301

Jiangsu Simcere Pharmaceutical Co., Ltd

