4.6.3. Clinical Laboratory Tests

Hematology and blood chemistry test results at baseline and each visit time point and corresponding changes from baseline will be summarized descriptively and listing will be provided in detail. CTCAE grades for hematology and blood chemistry will be determined according to the laboratory parameter CTCAE criteria(see Appendix 3). CTCAE Version 5.0 will be used for grading. According to CTCAE Version 5.0, CTCAE grading of some items requires clinical diagnosis or joint judgment of clinical diagnosis and values, which cannot be completely divided by programming, such as hyperglycemia, hypokalemia, hypophosphatemia, hyponatremia and hyperuricemia, CTCAE Version 4.03 will be used for grading. Patients' changes from baseline CTCAE grade to worst postdose CTCAE grade will be summarized using cross-classification tables. Grade 3 or 4 hematology and blood chemistry laboratory abnormalities occurring during treatment will also be summarized separately, as appropriate. Urinalysis results will be presented in listings only.

Actual study days for patients may differ from planned study days between the first dose of study drug in each cycle and the scheduled visit date. In this case, visit-based summaries will categorize assessments based on visit within time window as shown in Appendix 4.

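### As printed, SAP Appendix 3 gives a triglyceride result above 1000 mg/dL (11.4 mmol/L) no grade unless it is judged life-threatening

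*SAP*

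**What the plan says.** SAP section 4.6.3 (Clinical Laboratory Tests) makes Appendix 3 the source of laboratory grades: "CTCAE grades for hematology and blood chemistry will be determined according to the laboratory parameter CTCAE criteria(see Appendix 3". The grades feed two outputs. The first is the shift table: "Patients' changes from baseline CTCAE grade to worst postdose CTCAE grade will be summarized using cross-classification tables". The second is a separate summary of Grade 3 or 4 hematology and chemistry abnormalities during treatment, produced as appropriate.

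In the triglyceride row of SAP section 5.3 (Appendix 3):

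- Grade 1 runs from 150 to 300 mg/dL (1.71 to 3.42 mmol/L).
- Grade 2 is "> 300 mg/dL to 500 mg/dL".
- Grade 3 is "> 500 mg/dL to 1000 mg/dL", in the second unit "or > 5.7 mmol/L to 11.4" mmol/L.
- Grade 4 is "Life Threatening", with no number legible.

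Section 4.6.3 accepts that some grades need a clinical diagnosis and cannot be fully programmed. For these it turns to the older criteria: "such as hyperglycemia, hypokalemia, hypophosphatemia, hyponatremia and hyperuricemia, CTCAE Version 4.03 will be used for grading". Triglycerides are not named there, and their row has no 4.03 label, whereas the hyperglycemia, hypokalemia, hypophosphatemia and hyponatremia rows do.

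**The concern.** Grade 3 has a closed upper limit and Grade 4 has no numeric entry point. A grading program that works from values alone would give Grade 3 at 1000 mg/dL and nothing at 1001 mg/dL, so a more extreme result would rank below a moderate one. The SAP has no rule for a value that meets no grade, and describes no step for obtaining a life-threatening judgment on a laboratory value. SAP section 4.11 says only that missing data are generally not imputed, which does not settle it.

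Triglycerides are in the chemistry panel (Protocol section 7.2.1). Chemistry is repeated in Cycle 1 and twice in each later cycle (Protocol sections 9.1 and 9.2), so the row will be used. At stake is an under-count in one row of the laboratory grade tables. The error, where it occurs, can only make a patient look less abnormal.

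**Working it through.** **1. Is the 1000 mg/dL limit a unit slip?** The row's own factor is 1.71 / 150 = 0.0114 mmol/L per mg/dL. Applied to each cut-point:

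| mg/dL | × 0.0114 | Printed mmol/L |
|---|---|---|
| 150 | 1.71 | 1.71 |
| 300 | 3.42 | 3.42 |
| 500 | 5.70 | 5.7 |
| 1000 | 11.40 | 11.4 |

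All four limits agree, so the cap on Grade 3 is consistent in both units.

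**2. The row applied literally.**

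| Value (mg/dL) | Grade from value alone | Grade if also judged life-threatening |
|---|---|---|
| 500 | 2 | – |
| 501 | 3 | – |
| 1000 | 3 | – |
| 1000.1 | none | 4 |
| 1200 | none | 4 |
| 5000 | none | 4 |

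The gap is every value above 1000 mg/dL that does not carry the clinical judgment.

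**3. Effect on a patient's worst grade.** Assumptions: ungraded values are passed over when the worst grade is picked (the SAP does not say), and no life-threatening judgment is recorded. A value of 12.0 mmol/L is 12.0 / 0.0114 = 1053 mg/dL, inside the gap.

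| Post-dose values (mmol/L) | Worst grade as printed | In Grade 3 or 4 summary? | Worst grade if Grade 3 is open-ended |
|---|---|---|---|
| 6.0, then 12.0 | 3 | yes | 3 |
| 5.0, then 12.0 | 2 | no | 3 |
| 12.0 only | none | no | 3 |

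**4. Comparison with other rows of Appendix 3.**

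- Albumin and hemoglobin also have a clinical-only Grade 4, but Grade 3 is open-ended (below 20 g/L and below 80 g/L). Albumin of 5 g/L and hemoglobin of 40 g/L both still give Grade 3.
- Hypermagnesemia gives Grade 4 a number (above 8.0 mg/dL; above 3.30 mmol/L) next to the clinical wording.
- Among rows with a clinical-only Grade 4, only triglycerides combine it with a closed Grade 3.
- Hypomagnesemia has a related fault. Grades 3 and 4 print the same band, 0.9 to 0.7 mg/dL (0.4 to 0.3 mmol/L). A value of 0.8 mg/dL meets both grades, and 0.6 mg/dL meets neither.

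**5. Size.** The documents do not say how often triglycerides exceed 1000 mg/dL. Taking 0 to 1 patients of about 80 as an assumption, the share affected is 0 to 1/80 = 1.25% overall, or at most 1/40 = 2.5% of one arm.

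**The case against.** The strongest objection is that the gap may come from text extraction. A stray letter C sits beneath the Grade 4 entry in the extracted text, the bilirubin Grade 4 cell nearby has lost words, and the cholesterol row is scrambled. A lost number is plausible but not shown: the legible entry has none. This objection stands in part, and is why the original table must be checked first.

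Second, the list of items graded under version 4.03 is introduced as examples, and Appendix 3 says version 5.0 is used primarily, so a programmer might close the gap from outside the SAP. That is possible, but the SAP states no such rule for triglycerides.

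Third, a reader might infer that the highest triglyceride results drop out of the safety tables, leaving safety reporting falsely reassuring. The documents do not support this. The SAP does not say how ungraded values are tabulated. A patient with another value in the Grade 3 band stays in the Grade 3 or 4 summary, and a result judged life-threatening is Grade 4. Section 4.6.3 also provides descriptive summaries of chemistry results and full listings. Clinically significant laboratory abnormalities are recorded as adverse events (Protocol section 8.1) and summarized under SAP section 4.6.2. This objection stands in full and limits the point to the laboratory grade tables.

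Fourth, one might conclude that Grade 4 simply needs the number 1000 mg/dL. The documents do not show that this is what the named CTCAE version intends, and it could label a result without symptoms as Grade 4. An open-ended Grade 3 has a precedent in the same appendix.

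**Conclusion.** The point holds in a limited form. As printed, a triglyceride result above 1000 mg/dL (11.4 mmol/L) without a life-threatening judgment meets no grade. The patient could then be under-graded in the baseline-to-worst table, and would be absent from the Grade 3 or 4 laboratory summary if no other value is Grade 3 or 4.

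This rests on three assumptions: the Grade 4 cell has no number in the original table, grades are derived from values as section 4.6.3 describes, and no unwritten rule fills the gap.

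The consequence is minor, probably one table entry or none. Triglycerides are neither an endpoint (Protocol section 2.2) nor an adverse event of special interest (Protocol section 8.9). The primary endpoint, sample size, type I error and adverse event tables are untouched. It is worth correcting because it is cheap and because the literal rule puts a more extreme value below a moderate one.

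**What to change.** 1. Check the triglyceride Grade 4 cell in the original Appendix 3. If it has a number that continues from 1000 mg/dL, no change to that row is needed.
2. If it has none, make Grade 3 open-ended (> 500 mg/dL; > 5.7 mmol/L), as in the albumin and hemoglobin rows, and keep Grade 4 for life-threatening cases. Alternatively, set Grade 4 at > 1000 mg/dL (> 11.4 mmol/L) if the sponsor confirms that its named CTCAE version supports it. With either change, every value from 150 mg/dL upward has a grade.
3. In the same edit, check the hypomagnesemia row against the named CTCAE version, so that Grades 3 and 4 no longer share a band and values below 0.7 mg/dL receive a grade.

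The triglyceride change costs one table cell and one line of grading code; the magnesium row is a similar small correction. Neither affects data collection or the conduct of the trial.

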1.3.1. Safety data

Exposure:

Overall, 435 individuals (168 healthy subjects and 267 cancer patients) have been exposed to Trilaciclib at various doses and over time: Note that since a small proportion of the same patients were included in Study G1T28-02 and Study G1T28-03 and their safety data in each study are considered separate patient records, a total of N = 272 cancer patients are reported in the Summary of Safety. Cancer patients were treated for a median duration of 4 cycles and 8.8% of patients received more than 10 cycles. Trilaciclib has been evaluated at doses between 6 and 700 mg/m². The sample size and duration of exposure in these trials provided an adequate safety database to assess the safety of Trilaciclib administered as a single agent (in healthy subjects) as well as with various chemotherapeutic agents (in cancer patients).

In the SCLC Safety Analysis Set, patients treated with Trilaciclib prior to chemotherapy were more able to receive the recommended dose on time than patients treated with placebo. This improvement was reflected in fewer dose reductions and higher relative dose intensity of chemotherapy administered in the Trilaciclib + Chemotherapy arm compared to the Placebo + Chemotherapy arm.

The percentage of patients who may discontinue treatment due to treatment-emergent adverse events (TEAEs), death, and investigator judgment was lower in patients receiving Trilaciclib than in patients receiving placebo.

Treatment-Emergent Adverse Events:

In the SCLC Safety Analysis Set, a significantly lower percentage of patients treated with Trilaciclib (59.8%) experienced Grade \geq 3 TEAEs compared with patients treated with placebo (83.1%);

In the SCLC Safety Analysis Set, a significantly lower percentage of patients treated with Trilaciclib (44.3%) experienced Grade 3 or 4 hematologic TEAEs compared with patients treated with placebo (77.1%);

In the SCLC Safety Analysis Set, TEAEs that occurred in $\geq 5\%$ of patients treated with Trilaciclib and at a $\geq 2\%$ higher occurrence than placebo included fatigue (33.6% and 27.1% in the Trilaciclib + Chemotherapy and Placebo + Chemotherapy arms, respectively), pyrexia (13.9% and 11.0%), headache (13.1% and 9.3%), hypokalemia (10.7% and 5.9%), infusion-related reaction (8.2% and 1.7%), upper abdominal pain (6.6% and 2.5%), peripheral edema (6.6% and 4.2%), rash (6.6% and 4.2%), and hyperglycemia (5.7% and 3.4%);

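### SAP Appendix 3 prints the SI hyperglycaemia limits in mol/L instead of mmol/L; read literally, every SI result above normal is Grade 1 and Grades 2 to 4 cannot occur

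*SAP*

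**What the plan says.** SAP section 4.6.3 makes Appendix 3 the working rule: "CTCAE grades for hematology and blood chemistry will be determined according to the laboratory parameter CTCAE criteria". It names hyperglycaemia among the items graded by CTCAE 4.03, because version 5.0 cannot be fully programmed for them. The grades feed a cross-tabulation of baseline against worst post-dose grade and, as appropriate, a separate summary of Grade 3 or 4 abnormalities.

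The hyperglycaemia row of Appendix 3 gives each limit twice, in mg/dL and in SI units:

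- Grade 1: "Fasting blood glucose greater than upper limit of normal - 160 mg/dL", or "Fasting blood glucose greater than upper limit of normal - 8.9 mol/L".
- Grade 2: above 160 to 250 mg/dL, or "fasting plasma glucose greater than 8.9-13.9 mol/L".
- Grade 3: above 250 to 500 mg/dL, or "fasting plasma glucose greater than 13.9-27.8 mol/L".
- Grade 4: "Fasting glucose greater than 500 mg/dL or 27.8 mol/L".

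The hypoglycaemia row gives the same analyte in mmol/L; its Grade 2 is "< 55 - 40 mg/dL; < 3.0 - 2.2 mmol/L".

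Protocol section 7.2.1 lists glucose in the chemistry panel and has it measured at local laboratories. It states no reporting unit and does not mention fasting.

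**The concern.** The SI limits and the mg/dL limits in each hyperglycaemia cell are meant to be the same thresholds, and they are not. Since section 4.6.3 sends the programmer to this table, the error sits in a rule that will be executed and not in background text. The documents do not fix a reporting unit, so SI results are not excluded.

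At stake is the severity shown for raised glucose in the laboratory shift tables and in the Grade 3/4 summary.

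**Working it through.** **Inputs.** From the hyperglycaemia row: 160, 250 and 500 mg/dL, paired with 8.9, 13.9 and 27.8 printed as mol/L. From the hypoglycaemia row: 55, 40 and 30 mg/dL, paired with 3.0, 2.2 and 1.7 mmol/L. Not in the documents: the molar mass of glucose, 180.156 g/mol (a physical constant), and the upper limit of normal (ULN), assumed here to be 5.6, 6.1 or 7.0 mmol/L.

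**Step 1: the SAP's own conversion.** Divide mg/dL by the printed SI number.

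- Hypoglycaemia (mmol/L): 55/3.0 = 18.33; 40/2.2 = 18.18; 30/1.7 = 17.65.
- Hyperglycaemia (printed mol/L): 160/8.9 = 17.98; 250/13.9 = 17.99; 500/27.8 = 17.99.

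Both rows use about 18 mg/dL per unit, so the unit is the same in both, although one is labelled mmol/L and the other mol/L.

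**Step 2: conversion from molar mass.** mmol/L = mg/dL × 10 / 180.156.

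- 160 mg/dL = 8.88 mmol/L
- 250 mg/dL = 13.88 mmol/L
- 500 mg/dL = 27.75 mmol/L

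Read as mmol/L, the printed 8.9, 13.9 and 27.8 agree to within 0.3%. Read as mol/L, they do not reproduce: 8.9 mol/L is 8.9 × 1000 × 180.156 / 10 = 160,339 mg/dL, and the other two are 250,417 and 500,834 mg/dL. Each is about 1,002 times the mg/dL limit beside it, which is the factor of 1000 plus rounding.

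**Step 3: literal application.** Grade 1 runs from ULN to 8.9 mol/L, and the higher grades need more than 8.9, 13.9 and 27.8 mol/L.

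| Result (mmol/L) | Same in mg/dL | Same in mol/L | Grade by mg/dL limit | Grade by mmol/L limit | Grade by printed mol/L limit |
|---|---|---|---|---|---|
| 7.5 | 135 | 0.0075 | 1 | 1 | 1 |
| 10 | 180 | 0.010 | 2 | 2 | 1 |
| 15 | 270 | 0.015 | 3 | 3 | 1 |
| 30 | 540 | 0.030 | 4 | 4 | 1 |

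The pattern is the same for all three assumed ULN values. The two limbs of one cell therefore give different grades to the same sample as soon as it exceeds 8.9 mmol/L.

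**The case against.** The strongest reply is that this is a transparent misprint. The correct mg/dL limit stands in every cell, the hypoglycaemia row of the same table uses mmol/L, and the row is labelled with the CTCAE version it follows. A competent programmer would probably notice. One who compared mmol/L results with the bare numbers 8.9, 13.9 and 27.8 would get the right grades anyway. Section 4.6.3 also summarises chemistry values and their changes from baseline and lists them in detail, so severe values stay visible whatever their grade. All of this stands, and it keeps the point small. It does not make the printed rule right, and a programmed grading table should not depend on someone quietly departing from it.

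A reader might go further in four ways that the documents do not support.

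- **That SI results would receive no grade, or that hyperglycaemia would show as 0%.** Grade 1 begins at ULN, so raised SI results are graded, but too low. Only Grades 2 to 4 are empty.
- **That the limits are 1000 times any possible value.** The factor applies to the matching mg/dL limit. Against 27.8 mmol/L (500 mg/dL), 8.9 mol/L is about 321 times as high.
- **That the background imbalance of 5.7% against 3.4% in protocol section 1.3.1 is at risk.** Those are rates of treatment-emergent adverse events. In this trial adverse events are graded by the investigator under CTCAE 5.0 (protocol section 8.5) and summarised under SAP 4.6.2. Appendix 3 governs only the programmed laboratory grades.
- **That non-fasting samples would be over-graded and a treatment difference diluted.** The hyperglycaemia limits are worded for fasting glucose, and the protocol text is silent on fasting. Silence does not show that samples were taken after meals, and the documents give no figure from which to size such an effect.

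**Conclusion.** The unit is wrong as written in all four hyperglycaemia grades, by a factor of 1000, and the SAP's own figures show that mmol/L is meant. Applied literally to SI results, the rule puts every value above ULN in Grade 1 and makes Grades 2 to 4 unreachable, so the glucose lines of the shift tables and of the Grade 3/4 summary would understate severity in both arms.

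This rests on two conditions that the documents leave open: that some laboratories report in SI units, and that the program uses the SI limb as printed. The share of patients affected cannot be computed, because neither the reporting units nor the expected glucose distribution is given. The consequence is confined to descriptive laboratory safety tables. No primary or key secondary endpoint, test or decision depends on it. This is a minor correction, worth making because it is certain and free.

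**What to change.** In SAP Appendix 3, change mol/L to mmol/L in the four hyperglycaemia cells and leave the numbers and the mg/dL limits as they are. If the grading program already exists, confirm which unit it uses; the four values in the table above serve as test cases and should return Grades 1, 2, 3 and 4.

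Separately, unless the case report form does record it, add a footnote to the glucose grade tables saying that fasting status was not recorded although the limits are worded for fasting glucose. Do not withhold grades from samples of unknown fasting status: no fasting record appears in the protocol text, so that could remove most hyperglycaemia grades and lose more safety information than the misprint does.

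The cost is an editorial correction to the SAP and one footnote, with no new data collection and no change to any other analysis.
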